5 STUDY DESIGN

5.1 Overall Design

CA2099ER Global Revised Protocol 01

[figure not shown]
Implementation of CA2099ER Global Revised Protocol 01 stops further randomization into Arm B. Participants previously randomized to Arm B continue with Arm B treatment and continue with Arm B clinical planned events, per protocol.

This is an open label, randomized trial of nivolumab combined with cabozantinib (doublet regimen) versus sunitinib in participants with previously untreated (first line) advanced or metastatic RCC. Participants will be randomized between Arm A and Arm C in a 1:1 ratio with approximately 638 participants (319 per arm) capped at approximate 25% to represent the normal frequency of favorable risk group in mRCC. The rest of the randomized participants will provide approximately 478 intermediate/poor risk randomized participants (239 per arm). Participants will be stratified at the time of randomization by IMDC prognostic score (0 [favorable risk] versus-1-

2 [intermediate risk] versus 3-6 [poor risk]), PD-L1 tumor expression ($\geq 1\%$ versus $< 1\%$ or indeterminate), and region (US/Canada/Western Europe/Northern Europe versus rest of the world [ROW]).

The study design schematic is presented in Figure 5.1-1.

Figure 5.1-1: Study Design Schematic

Abbreviations: DMC= data monitoring committee; IMDC= International Metastatic Renal Cell Carcinoma Database Consortium; IV=intravenous; PD-L1= programmed death-ligand 1; PO= orally by mouth; Pts=patients/participants; Q2W=every 2 weeks; Q3W=every 3 weeks; QD= once daily; RCC=renal cell carcinoma.

Arm B is shown in the design schematic because after implementation of Revised Protocol 01, there will be patients on treatment from the original protocol version 08 Mar 2017.

This study will consist of 3 stages: screening, treatment, and follow up phase.

Screening stage: Screening begins by establishing the participant’s initial eligibility and signing of the informed consent (ICF). Sufficient, recent tumor tissue, preferably obtained within 3 months but no more than 12 months prior to enrollment, from a metastatic tumor lesion or from a primary tumor lesion which has not been previously irradiated (formalin-fixed paraffin-embedded block or 20 unstained slides: a minimum of 10 slides, obtained from core biopsy, punch biopsy, excisional biopsy or surgical specimen) will be submitted to the central laboratory. Upon receipt of the tumor sample, the central lab will determine PD-L1 expression level by immunohistochemistry (IHC) testing (see Section 9.8.2). In order to be randomized in the Interactive Response Technology (IRT) system, a participant must be classified as PD-L1 expression $\geq 1\%$, PD-L1 expression $< 1\%$,

or PD-L1 expression indeterminate. Sites will be informed when the submitted tumor sample is insufficient for PD-L1 testing by the central lab.

Participants will be assessed for complete study eligibility prior to randomization as specified in [Section 2](#).

The Screening stage ends with either confirmation of full eligibility and randomization for the participant or with the confirmation that the participant is a screen failure. This study permits the re-enrollment of a participant that has discontinued the study as a pre-treatment failure prior to randomization. If re-enrolled, the participant must be re-consented. A new participant identification number will be assigned by IRT at the time of re-enrollment.

Treatment stage:

CA2099ER Global Revised Protocol 01

Implementation of CA2099ER Global Revised Protocol 01 stops further randomization into Arm B. Participants previously randomized to Arm B continue with Arm B treatment and continue with Arm B clinical planned events, per protocol.

The Treatment stage begins when the randomization call is made into the IRT. The participant is randomly assigned to 1 of the 2 treatment arms as noted in the study schematic above.

- Arm A (Doublet): Nivolumab 240 mg flat dose IV Q2W + Cabozantinib 40 mg PO QD
 - Nivolumab to be continued until disease progression or unacceptable toxicity with maximum treatment of 2 years from the first dose in Cycle 1
 - Cabozantinib to be continued until disease progression or unacceptable toxicity
- Arm C: Sunitinib 50 mg PO QD for 4 weeks, followed by 2 weeks off, per cycle. Cycles to be continued until progression or unacceptable toxicity

- Note - Randomization to Arm B stops with implementation of approved CA2099ER Global Revised Protocol 01. Treatment B (below) continues only for participants randomized to Arm B prior to implementation of Global Revised Protocol 01
 - Arm B (Triplet): Nivolumab 3mg/kg IV + Ipilimumab 1 mg/kg IV, both Q3W x 4 doses + Cabozantinib 40 mg PO QD
 - Then Nivolumab 240 mg flat dose IV Q2W + Cabozantinib 40 mg PO QD
 - Nivolumab to be continued until disease progression, unacceptable toxicity, or a maximum of 2 years from the first dose in Cycle 1
 - Cabozantinib to be continued until progression or unacceptable toxicity

Study treatment must begin within 3 days (72 hours) of randomization. Participants in Arm A will continue nivolumab until progression, unacceptable toxicity, withdrawal of consent, or a maximum of 2 years from the first dose in Cycle 1, whichever occurs first. Cabozantinib (Arm A) may be continued until progression, unacceptable toxicity, or withdrawal of consent, whichever occurs first, and may extend beyond 2 years from the first dose in Cycle 1. See [Table 7.1-1](#) and

Table 7.1-2 for the dosing schedule. Study drugs may be delayed for toxicity (See Section 7.4.1). Treatment may be continued beyond investigator-assessed progression if the investigator confirms that the participant meets the criteria specified in Section 8.1.4.

A negative pregnancy test should be documented within 24 hours prior to the initial dose of the investigational product and then performed every 4 weeks \pm 7 days during treatment. On-study laboratory assessments should be drawn within 72 hours prior to dosing and will be assessed at the local laboratory.

Tumor assessments will occur in accordance with Section 2 and Section 9.1.2 until progression has been assessed by the investigator **and** confirmed by the blinded independent central review (BICR). Each site must submit scans on a rolling basis, preferably within 7 days of image acquisition, to a third-party vendor for BICR. If progression is assessed by the investigator, the site will inform the radiology vendor so that the BICR assessment of progression can be performed. The BICR assessment of progression will be completed, and the results provided to the site, within approximately 14 days, as specified in Section 9.1.2.

Adverse event assessments should be documented at each clinic visit.

The Treatment stage ends when the participant is discontinued from study therapy.

Follow-up stage: The Follow-up stage begins when the decision to discontinue a participant from study therapy is made (no further treatment with study therapy). Participants must be followed for at least 100 days after last dose of study treatment. Follow-up visit #1 (FU1) should occur 30 days from the last dose (\pm 7) days or can be performed on the date of discontinuation if that date is greater than 42 days from last dose. Follow-up visit #2 (FU2) occurs approximately 100 days (\pm 7 days) from last dose of study drug. Both Follow Up visits should be conducted in person. AEs will be followed until the toxicities resolve, return to baseline, or are deemed irreversible.

Participants who discontinued study treatment without BICR confirmed radiographic progression will continue to have tumor assessments performed according to the frequency described in Sections 2 and 9.1.2, even if new anti-tumor therapy has been initiated. If progression is assessed by the investigator, the site will inform the radiology vendor, so that the BICR assessment of progression can be performed. Participants whose progression is not confirmed by the BICR will be required to continue tumor assessments (if clinically feasible) according to the protocol-specified schedule or sooner if clinically indicated until BICR confirms progression on a subsequent tumor assessment (See Section 9.1.2.2 for additional details).

After the Follow-up 2 Visit, all participants will be followed for overall survival status every 3 months (\pm 14 days) until death, withdrawal of consent, loss to follow-up, or end of study. Survival status can be ascertained in person or by telephone contact. If new anti-tumor therapy is

initiated for either progression or a secondary malignancy at any time during this period, this and all other pertinent data obtained should be recorded on the appropriate Case Report Form (CRF).

5.1.1 Data Monitoring Committee and Other External Committees

To provide independent oversight of safety, efficacy, and study conduct, a data monitoring committee (DMC) will be instituted. The DMC will meet regularly to ensure that participant safety is carefully monitored, including a safety assessment after the first 30 participants are randomized including participants in Arm B prior to global Revised Protocol 01 and are followed for at least 6 weeks and then again after the first 75 participants are randomized and followed for at least 6 weeks. The DMC will convene additional ad hoc meetings if necessary. Following each meeting, the DMC will recommend continuation, modification, or discontinuation of the study based on observed toxicities. The DMC will also review the interim analysis results and inform BMS whether stopping criteria for superiority are met at that time. A separate DMC charter will describe the activities of this committee in more detail.

Blinded independent central review (BICR) will be utilized in this study for determination of PFS endpoint. The BICR will review all available tumor assessment scans for all randomized participants. Details of BICR responsibilities and procedures will be specified in the BICR charter.

5.2 Number of Participants

Approximately 850 participants will be enrolled in order to randomize approximately 638 participants (319 per Arm A and per Arm C). The number of randomized participants with favorable risk disease will be capped at approximately 25% (160) participants.

5.3 End of Study Definition

The start of the trial is defined as the first visit for the first participant screened. End of trial is defined as the last visit or scheduled procedure shown in the Schedule of Activities for the last participant. Study completion is defined as the final date on which data for the endpoint of overall survival was or is expected to be collected, if this is not the same.

[REDACTED]

6 STUDY POPULATION

For entry into the study, the following criteria **MUST** be met.

6.1 Inclusion Criteria

1) Signed Written Informed Consent

- a) Participants must have signed and dated an IRB/IEC approved written informed consent form in accordance with regulatory and institutional guidelines. This must be obtained before the performance of any protocol related procedures that are not part of normal participant care.
- b) Participants must be willing and able to comply with scheduled visits, treatment schedule, and laboratory testing.

2) Type of Participant and Target Disease Characteristics

- a) Histological confirmation of RCC with a clear-cell component, including participants who may also have sarcomatoid features
- b) Advanced (not amenable to curative surgery or radiation therapy) or metastatic (AJCC Stage IV) RCC
- c) No prior systemic therapy for RCC with the following exception:
 - i) One prior adjuvant or neoadjuvant therapy for completely resectable RCC if such therapy did not include an agent that targets VEGF or VEGF receptors and if recurrence occurred at least 6 months after the last dose of adjuvant or neoadjuvant therapy.
- d) Karnofsky Performance Status (KPS) \geq 70% (See [Appendix 7](#))
- e) Measurable disease as per RECIST v1.1 per investigator. (See [Appendix 8](#))
- f) Either a formalin-fixed, paraffin-embedded (FFPE) tissue block or unstained tumor tissue sections, preferably obtained within 3 months but no more than 12 months prior to enrollment, with an associated pathology report, must be submitted to the central laboratory during screening. Biopsy should be excisional, incisional or core needle. Fine needle aspiration is unacceptable for submission. In participants who received prior adjuvant or neoadjuvant therapy, the tumor sample must have been obtained after completion of adjuvant or neoadjuvant therapy. Upon receipt of the tumor sample, the central lab will determine PD-L1 expression level by IHC testing (see [Section 9.8.2](#)). In order to be randomized in the IRT system, a participant must be classified as PD-L1 expression \geq 1%, PD-L1 expression $<$ 1%, or PD-L1 expression indeterminate. Sites will be informed when the submitted tumor sample is insufficient for PD-L1 testing by the central lab.

- g) Participants with favorable, intermediate and poor risk categories will be eligible for the study. To be eligible for the Intermediate and Poor-Risk cohort, at least one of the following prognostic factors as per International Metastatic RCC Database Consortium (IMDC) must be present: (See [Appendix 6](#))
- i) KPS equal to 70%
 - ii) Less than 1 year from initial diagnosis (including original localized disease if applicable) to randomization
 - iii) Hemoglobin < lower limit of normal (LLN)
 - iv) Corrected calcium concentration > 10 mg/dL
 - v) Absolute neutrophil count > ULN
 - vi) Platelet count > ULN

If none of the above factors are present, participants are only eligible for the favorable-risk cohort. Approximately 160 favorable risk participants will be randomized. Enrollment of favorable risk participants may be closed earlier than enrollment for intermediate and poor risk participants.

3) Age and Reproductive Status

- a) Males and Females, ages 18 or age of majority
- b) Women of childbearing potential (WOCBP) must have a negative serum or urine pregnancy test (minimum sensitivity 25 IU/L or equivalent units of HCG) within 24 hours prior to the start of study treatment
- c) Women must not be breastfeeding
- d) Women of childbearing potential (WOCBP) must agree to follow instructions for method(s) of contraception for the duration of study treatment and 5 months after the last dose of study treatment (ie, 30 days [duration of ovulatory cycle] plus the time required for the investigational drug to undergo approximately five half-lives).
- e) Males who are sexually active with WOCBP must agree to follow instructions for method(s) of contraception for the duration of study treatment and 7 months after the last dose of study treatment (ie, 90 days [duration of sperm turnover] plus the time required for the investigational drug to undergo approximately five half-lives).
- f) Azoospermic males are exempt from contraceptive requirements. WOCBP who are continuously not heterosexually active are also exempt from contraceptive requirements, and still must undergo pregnancy testing as described in this section.

Investigators shall counsel WOCBP, and male participants who are sexually active with WOCBP, on the importance of pregnancy prevention and the implications of an unexpected pregnancy. Investigators shall advise on the use of highly effective methods of contraception ([Appendix 4](#)) which have a failure rate of < 1% when used consistently and correctly.

6.2 Exclusion Criteria

1) Medical Conditions

- a) Any active CNS metastases. Participants with treated, stable CNS metastases for at least 1 month are eligible as long as they meet the following criteria:

Treated CNS metastases are defined as having no ongoing requirement for corticosteroids for at least 2 weeks prior to randomization and no evidence of progression or hemorrhage after treatment completed at least 1 month prior to randomization, as ascertained by clinical examination and brain imaging (MRI or CT). (Stable dose of anticonvulsants is allowed). Treatment for CNS metastases may include whole brain radiotherapy, radiosurgery (eg, RS, gamma knife, LINAC, or equivalent) or a combination as deemed appropriate by the treating physician. Participants with CNS metastases treated by neurosurgical resection or brain biopsy performed within 1 month prior to randomization are not eligible. Baseline imaging of the brain is required within 28 days prior to randomization.

- b) Any active, known or suspected autoimmune disease. Participants with type I diabetes mellitus, hypothyroidism only requiring hormone replacement, skin disorders (such as vitiligo, psoriasis, or alopecia) not requiring systemic treatment, or conditions not expected to recur in the absence of an external trigger (e.g. celiac disease) are permitted to enroll.
- c) Any condition requiring systemic treatment with either corticosteroids (> 10 mg daily prednisone equivalent) or other immunosuppressive medications within 14 days of randomization. Inhaled or topical steroids, and adrenal replacement steroid doses > 10 mg daily prednisone equivalent, are permitted in the absence of active autoimmune disease.
- d) Prior malignancy active within the previous 3 years except for locally curable cancers that have been apparently cured, such as basal or squamous cell skin cancer, superficial bladder cancer, or carcinoma in situ of the prostate, cervix, or breast
- e) Any tumor invading the SVC or other major blood vessels
- f) Any tumor invading the GI tract or any evidence of endotracheal or endobronchial tumor within 30 days prior to randomization
- g) Known history of positive test for human immunodeficiency virus (HIV) or known acquired immunodeficiency syndrome (AIDS). NOTE: Testing for HIV must be performed at sites where mandated locally (sites in Germany, see [Appendix 12](#)).
- h) Known medical condition (eg, a condition associated with diarrhea or acute diverticulitis, aortic aneurysm, aortic dissection) that, in the investigator's opinion, would increase the risk associated with study participation or study drug administration or interfere with the interpretation of safety results
- i) History of abdominal fistula, gastrointestinal perforation, intra-abdominal abscess, bowel obstruction, or gastric outlet obstruction within the past 6 months prior to randomization
- j) Impairment of gastrointestinal function or gastrointestinal disease that may significantly alter the absorption of cabozantinib or sunitinib (eg, malabsorptive disorder, ulcerative disease, uncontrolled nausea, vomiting, diarrhea, or small bowel resection)
- k) Serious, non-healing wound or ulcer within 30 days prior to randomization
- l) Evidence of active bleeding or bleeding susceptibility; or medically significant hemorrhage within prior 3 months prior to randomization
- m) Uncontrolled adrenal insufficiency
- n) History of cerebrovascular accident (CVA) including transient ischemic attack within the past 6 months prior to randomization

- o) History of deep vein thrombosis (DVT) or pulmonary embolism (PE) within past 6 months prior to randomization unless stable, asymptomatic, and treated with low molecular weight heparin (LMWH) for at least 3 weeks prior to randomization
- p) Any unstable cardiac arrhythmia within 6 months prior to randomization
- q) Prolongation of the Fridericia corrected QT (QTcF) interval defined as > 450 msec for males and > 470 msec for females, where $QTcF = QT / \sqrt[3]{RR}$ with triplicate measurements
- r) Poorly controlled hypertension (defined as systolic blood pressure (SBP) of > 150 mmHg or diastolic blood pressure (DBP) of > 90 mmHg), despite antihypertensive therapy
- s) History of any of the following cardiovascular conditions within 6 months of randomization: cardiac angioplasty or stenting, myocardial infarction, unstable angina, coronary artery by-pass graft surgery, symptomatic peripheral vascular disease, class III or IV congestive heart failure (CHF), as defined by the New York Heart Association (NYHA)
- t) Any radiologic or clinical evidence of pancreatitis within 30 days prior to randomization
- u) Inability to swallow oral medications

[REDACTED]

3) Physical and Laboratory Test Findings

- a) Ejection fraction $\leq 50\%$ on screening echocardiogram or MUGA
- b) WBC $< 2000/\mu\text{L}$

- c) Neutrophils < 1500/ μ L
- d) Platelets < 100 x 10³/ μ L
- e) Hemoglobin < 9.0 g/dL (support with transfusion is acceptable)
- f) Serum creatinine > 1.5 x ULN unless calculated creatinine clearance \geq 40 mL/min (using the Cockcroft-Gault formula)
- g) AST/ALT > 3.0 x ULN
- h) Total bilirubin > 1.5 x ULN (except participants with Gilbert Syndrome who must have a total bilirubin level of < 3.0 x ULN)
- i) Urine protein/creatinine ratio (UPCR) > 1.5, unless 24-hour urine protein is \leq 1.5 g
- j) INR > 1.5
- k) Any positive test result for hepatitis B virus or hepatitis C virus indicating presence of virus, eg, hepatitis B surface antigen (HBsAg) positive, or hepatitis C antibody (anti-HCV) positive (except if HCV-RNA negative)

4) Allergies and Adverse Drug Reaction

- a) History of allergy or hypersensitivity to study drug components
- b) No history of severe hypersensitivity to a monoclonal antibody

5) Other Exclusion Criteria

- a) Prisoners or participants who are involuntarily incarcerated. (Note: under specific circumstances, and only in countries where local regulations permit, a person who has been imprisoned may be included as a participant. Strict conditions apply and Bristol-Myers Squibb approval is required.)
- b) Participants who are compulsorily detained for treatment of either a psychiatric or physical (eg, infectious disease) illness

Eligibility criteria for this study have been carefully considered to ensure the safety of the study participants and that the results of the study can be used. It is imperative that participants fully meet all eligibility criteria.

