3 INTRODUCTION

Renal cell carcinoma (RCC) is the eighth most common cancer in the world with an increasing incidence.¹ Globally, RCC occurs in more than 330,000 cases with approximately a third of the patients succumbing to their disease. More than 100,000 deaths occur annually, as a result of progression of metastatic disease. Despite the earlier detection of smaller kidney tumors, the rate of RCC-related mortality has increased suggesting that recurrence and advanced disease are responsible for mortality.^{2,3} With the rise in RCC incidence, as well as mortality and morbidity associated with advanced RCC, medical need in this population remains a priority.

Over the last decade, an increased understanding of the biology of RCC has led to development of multiple agents that target specific growth pathways. The vascular endothelial growth factor (VEGF) pathway and targeted serine/threonine protein kinase therapies that block the mammalian target of rapamycin (mTOR) have been found to be important targets in RCC disease. Global health authorities (HAs) have approved multiple drugs targeting these pathways, including anti-VEGF agents, such as pazopanib, sorafenib, sunitinib, cabozantinib, and bevacizumab, and mTOR pathway inhibitors, such as temsirolimus and everolimus.⁴ Additionally, recent innovation of treating cancer with immunotherapies has also expanded treatment options. Nivolumab, an anti-PD-1 antibody, given as monotherapy or in combination with the anti-CTLA-4 antibody, ipilimumab, has demonstrated clinical activity in multiple tumor types, including RCC.

To better understand treatment and patient outcomes, several academic groups have identified variables associated with survival and created prognostic models in mRCC. These risk models are commonly used for choosing therapies or selecting patients for treatment in clinical trials. The International Metastatic Renal Cell Carcinoma Database Consortium (IMDC) model stratifies patients into 3 prognostic groups, based on 6 adverse prognostic factors, into favorable (0 factors), intermediate (1-2 factors), and poor risk (3-6 factors) groups.⁵ The currently available first-line agents for mRCC, which target the VEGF pathway, have shown limited efficacy in the intermediate and poor risk populations, yielding median overall survival of approximately 2 years or less.

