9 STUDY ASSESSMENTS AND PROCEDURES

CA2099ER Global Revised Protocol 01

Implementation of CA2099ER Global Revised Protocol 01 stops further randomization into Arm B. Participants previously randomized to Arm B continue with Arm B treatment and continue with Arm B clinical planned events, per protocol.

- Study procedures and timing are summarized in the Schedule of Activities.
- Protocol waivers or exemptions are not allowed.
- All immediate safety concerns must be discussed with the Sponsor immediately upon occurrence or awareness to determine if the participant should continue or discontinue treatment.
- Adherence to the study design requirements, including those specified in the Schedule of Activities, is essential and required for study conduct.
- All screening evaluations must be completed and reviewed to confirm that potential participants meet all eligibility criteria before randomization. The investigator will maintain a screening log to record details of all participants screened and to confirm eligibility or record reasons for screening failure, as applicable.
- Procedures conducted as part of the participant's routine clinical management (eg, blood count) and obtained before signing of informed consent may be utilized for screening or baseline purposes provided the procedure meets the protocol-defined criteria and has been performed within the timeframe defined in the Schedule of Activities.

Additional measures, including non-study required laboratory tests, should be performed as clinically indicated or to comply with local regulations. Laboratory toxicities (eg, suspected drug induced liver enzyme evaluations) will be monitored during the follow-up phase via on site/local labs until all study drug related toxicities resolve, return to baseline, or are deemed irreversible.

If a participant shows pulmonary-related signs (hypoxia, fever) or symptoms (eg, dyspnea, cough, fever) consistent with possible pulmonary adverse events, the participant should be immediately

evaluated to rule out pulmonary toxicity, [REDACTED]
[REDACTED]

Some of the assessments referred to in this section may not be captured as data in the eCRF. They are intended to be used as safety monitoring by the treating physician. Additional testing or assessments may be performed as clinically necessary or where required by institutional or local regulations.

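### Exclusion criterion 4b is worded as an entry condition, so read literally it points the wrong way for the list it sits in

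*Protocol*

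**What the plan says.** Protocol 6.2 is headed "6.2 Exclusion Criteria". Group 4, on allergies and adverse drug reactions, has two items:

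- 4a: "History of allergy or hypersensitivity to study drug components"
- 4b: "No history of severe hypersensitivity to a monoclonal antibody"

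The section closes with a strict instruction: "It is imperative that participants fully meet all eligibility criteria". Section 9 adds: "Protocol waivers or exemptions are not allowed".

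The criterion is relevant to the treatments given. The Introduction describes "Nivolumab, an anti-PD-1 antibody, given as monotherapy or in combination with the anti-CTLA-4 antibody, ipilimumab". Nivolumab is given in Arm A. Both antibodies are given to participants randomized to Arm B before Revised Protocol 01. Arm C receives sunitinib only.

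**The concern.** An exclusion list works in one direction: a person who meets an item cannot enter. Item 4b describes the acceptable state instead. Taken at its word, it turns away the ordinary candidate and lets past the one person it was presumably written to stop.

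This is operative eligibility text. It concerns a history that matters most for people who may be assigned an intravenous antibody, and the protocol asks for full compliance without waivers. What is at stake is whether sites, monitors and anyone who translates or programs an eligibility checklist all work from the same rule.

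**Working it through.** No arithmetic applies. The check is one of logic and of cross-reading.

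**Step 1. Apply 4b as an exclusion.**

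| Candidate's history of severe reaction to a monoclonal antibody | Is 4b, as worded, met? | Result in an exclusion list |
|---|---|---|
| Absent | Yes | Barred |
| Present | No | Not barred by 4b |

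**Step 2. Compare polarity with the neighbouring items.** Item 4a names the condition that excludes. So do the other history items in 6.2, for example 1n: "History of cerebrovascular accident (CVA) including transient ischemic attack within the past 6 months prior to randomization". Among the visible items, 4b is the only one worded as the desired state.

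**Step 3. See whether the lead-in rescues it.** Section 6 opens with "For entry into the study, the following criteria" and says that they must be met. That sentence stands above both the inclusion and the exclusion lists. If it turned 4b into an entry requirement, it would do the same to every other item in 6.2, including 1n and 4a. It may explain how the wording arose, but it does not make the list consistent.

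**Step 4. Look for a correction elsewhere.**

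- The key exclusions in the synopsis do not mention this criterion.
- The change summaries for Revised Protocols 01 and 02 list edits to several items in 6.2, and 4b is not among them.
- The only exclusion criterion that Appendix 12 alters is the one on HIV.

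**Step 5. Ask who is left uncovered if 4b does not do its job.**

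- Hypersensitivity to nivolumab, ipilimumab or another study drug component: covered by 4a.
- Prior treatment with antibodies against PD-1, PD-L1, PD-L2, CD137 or CTLA-4, with other agents aimed at T-cell co-stimulation or checkpoint pathways, or with bevacizumab: excluded by the synopsis whatever the reaction was.
- A known medical condition that raises the risk of study drug: item 1h, but only in the investigator's opinion and without naming antibody reactions.
- A severe reaction to a monoclonal antibody outside those classes: named in no visible item except 4b.

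Item 2 of 6.2 is redacted, so its content could not be compared.

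**The case against.** The best reply is that nobody would apply the literal reading, because it would empty the trial. The intended direction is plain from 4a, from the other history items, and from Protocol 8.1.1, where a Grade 3 drug-related hypersensitivity or infusion reaction leads to permanent discontinuation of the antibody. Sites very probably read 4b as intended. That stands, and it limits the consequence to a wording error.

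Three stronger inferences are tempting, and the documents support none of them.

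- *All 638 randomized participants are eligibility deviations.* This is a sample size attached to a reading that defeats itself. SAP 7.2 programs three eligibility deviations: performance status, prior systemic treatment in the metastatic setting, and histology or stage. Item 4b is not among them. The PFS sensitivity analysis in SAP 7.5.2 that leaves out subjects with relevant deviations would move only if someone recorded a literal 4b failure as a non-programmable relevant deviation. Nothing suggests that.
- *The criterion cannot be audited.* A site can record the history and a monitor can check it. Only the direction of the rule is misstated.
- *People with such a history have no protection.* Item 4a, the prior-antibody exclusions and 1h narrow the gap. Participants are also monitored for infusion reactions (Protocol 7.1), which are managed by grade (7.4.4). Half of those planned for the two main arms (319 of 638) are assigned to Arm C and receive no antibody.

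The objection does not remove the error. The intended meaning has to be inferred from other items, in a protocol that asks for its criteria to be met in full.

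**Conclusion.** The point holds as a drafting error. Item 4b has the wrong polarity for the exclusion list, and no visible text corrects it. The gap that remains, if 4b is read literally, is confined to people with a severe reaction to a monoclonal antibody not already reached by 4a or the prior-antibody exclusions. For them, only the investigator's discretion under 1h stands at entry. The documents give no count of such people, so the size cannot be stated.

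Sample size, power, alpha, endpoints and the programmed deviation summary are unaffected. The conclusion rests on two assumptions: that the redacted item 2 of 6.2 does not already name this history, and that sites followed the evident intent. The documents cannot confirm either.

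**What to change.** Reconcile 4b with its heading and with 4a, so that it states the condition that excludes. Removing the leading negative would do this. It can go in an administrative letter or in the next amendment. The document history shows that Administrative Letter 01 was already used to correct typographical errors and inconsistencies.

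At the same time, confirm that site eligibility checklists, translations and any electronic eligibility forms carry the same polarity. If one of them copied the literal wording, check the records entered through it. The text change is one line and leaves the design and the SAP as they are. The checklist check is a short administrative task.
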